**All-cause mortality**

The cause of death will be based on all available information, including clinical documents, autopsy if available, and official death certificate.

### **3. TRIAL DESIGN**

#### **3.1 Trial Design**

APPLE is a feasibility pilot, open-label, randomized controlled clinical trial in 2 centers, Ottawa and Hamilton, Ontario. Pregnant women with antiphospholipid

syndrome and past late ( $\geq 10$  weeks gestation) or recurrent early ( $2 < 10$  weeks) pregnancy loss will be randomized to low-dose ASA daily (experimental arm) or prophylactic-dose LMWH/ASA (standard of care arm). Other than LMWH use, the two arms will have identical follow-up care.

The study consists of four periods: screening and randomization, antenatal follow-up, labour and delivery, and post-partum follow-up. Maximum time on study will vary between 34 and 52 weeks.

### **3.2 Screening, Baseline and Randomization**

Feasibility outcomes will be collected using detailed screening and enrollment logs. Screening logs will document reasons for ineligibility. We will also explore and document reasons for non-consent from patients and local investigators in order to refine the larger multicenter study.

Randomization is done within 7 days of completing the baseline assessment. Subjects who meet the inclusion/exclusion criteria and have signed informed consent will be assigned to one of the two treatment groups (ASA vs LMWH/ASA), stratified by pregnancy loss history and laboratory testing. Details on how a subject is randomized are provided in section 5.3.

Prior to randomization and study entry, a BHCG is needed to confirm the current pregnancy, if not already available. CBC and creatinine blood work will be drawn at baseline, if not previously available within the past 3 months. Past obstetrical history will be recorded.

Subjects can still be enrolled and randomized in the study if they only have one positive antiphospholipid antibody result. A second set of labs would then be drawn 12 weeks apart from the first set, and if the second set is positive they will continue in the study. If the second set is negative, the subject will be withdrawn from the study.

Within 7 days of enrollment, a baseline obstetrical ultrasound is recommended. If the subject is enrolled in early first trimester ( $< 6$  weeks gestation) then the ultrasound will be completed at 6-7 weeks gestation. Blood work will also be drawn on enrollment and stored to be tested in a central laboratory (lupus anticoagulant, anticardiolipin antibody, beta-2 glycoprotein antibody).

Each subject will receive education regarding LMWH administration, potential adverse effects and symptoms of VTE by clinic personnel (not research personnel), based on standard of care.

### **3.3 Antenatal Follow-Up**

The antenatal follow-up visit will take place at  $20 \pm 4$  weeks gestation. Study outcomes and/or adverse events will be assessed and documented. If available, obstetrical ultrasound results will be recorded.

The subject will be asked to bring the Patient Medication Diary to the follow-up visit. Using subject recall and the Medication Diary, treatment compliance will be documented.

For subjects randomized to LMWH/ASA, the suggested protocol is tinzaparin 4,500 IU sc daily until 20 weeks gestation, then tinzaparin 4,500 IU sc twice daily until 37 weeks gestation and ASA 81 mg po daily until delivery.

Use of trial medication beyond 37 weeks gestation is left up to the discretion of the treating physician. Discontinuing the study medication at 37 weeks will minimize the possibility of being anticoagulated at the time of delivery or epidural analgesia.

### **3.4 Labour and Delivery**

Subjects randomized to receive LMWH/ASA will be instructed to discontinue LMWH at 37 weeks, or at the onset of labour if they have not already done so.

For all subjects, information regarding labour, anaesthesia, delivery, complications, fetal weight and health at birth will be recorded. Outcomes of interest and adverse events will be recorded based on available hospital records.

Subjects who prefer to deliver at another hospital or at home, may participate in the study, so long as arrangements are made to collect the labour and delivery data retrospectively.

### **3.5 Postpartum Follow-up**

The use of postpartum LMWH and ASA prophylaxis will be left up to the treating physician, and will be documented. At the postpartum visit at 6-12 weeks postpartum, outcome events will be recorded up until 6 weeks postpartum. Adverse events requiring medical intervention will be followed until resolution or will be classified as chronic/ongoing after 90 days at the discretion of the investigator.

### **3.6 End of Study**

Study crossover, compliance, and early termination will be documented. Reasons for study crossover (patient or physician preference) will be documented. If a subject terminates the study early, ASA and/or LMWH will be left to the treating physician, and documented. Primary and secondary outcomes will be captured.

## **4. SELECTION AND WITHDRAWAL OF SUBJECTS**

### **4.1 Inclusion Criteria**

All of the following inclusion criteria must be met to be eligible: 1) confirmed pregnancy, 2) 18 years or older, 3) one or more clinical criteria as outlined below, 3) one or more laboratory criteria as outlined below, and 4) written informed consent.

Clinical criteria: Past history of pregnancy loss defined as either:

- A. Two or more unexplained\* pregnancy loss before the 10th week of gestation\*\*
- B. One or more unexplained\* pregnancy loss at or beyond the 10th week of gestation\*\*

**AND**

Laboratory Criteria: At least **one** positive laboratory test listed below that is positive on **two** or more occasions at least 12 weeks apart\*\*\*:

- A. Presence of lupus anticoagulant (LAC)

- B. Anticardiolipin antibody (aCL) of IgG or IgM with a titre > 99th percentile or > 40 GPL or MPL
- C. Anti-β2 glycoprotein antibody of IgG and/or IgM with a titre > 99th percentile

Subjects can initially be eligible for enrollment and randomization if they only have one positive lab result. A second set of labs would be drawn 12 weeks apart from the first lab result, and if the second set is positive they will continue in the study. If the second set is negative, the subject will be withdrawn from the study.

\*Examples of explained miscarriage or fetal loss include: loss associated with severe congenital malformations, chromosomal abnormalities, neonatal alloimmune haemolytic anaemia, recent CMV infection, positive fetal or placental Listeria cultures, and women with known abnormal uterine anatomy.

\*\*Determining timing of pregnancy loss: in reviewing the past obstetrical history the investigator will use the best available information (First, pathological examination of products of conception then ultrasound dating assessment at the time of pregnancy loss then medical documentation of timing of pregnancy loss then patient recall of timing of pregnancy loss) to determine the gestational age at the time of pregnancy loss.

\*\*\*According to the diagnostic criteria of APS, diagnosis should be avoided if more than 5 years is separated between positive antibody testing and a clinical manifestation, such as pregnancy loss

#### **4.2. Exclusion Criteria**

1. Greater than 11 weeks +6 days gestational age at time of randomization
2. Indication(s) for prophylactic or therapeutic-dose anticoagulation
  - a. Venous thromboembolism (VTE)
  - b. Arterial thromboembolism (ATE)
  - c. Small-vessel thrombosis
  - d. Mechanical heart valve
  - e. Other indication for prophylactic or therapeutic-dose anticoagulation, at the discretion of the treating physician
3. Contraindication to heparin or aspirin including:
  - a. History of known heparin or LMWH allergy
  - b. History of known aspirin allergy
  - c. History of HIT
  - d. History of osteoporosis
  - e. Major bleeding within 7 days\*.
  - f. Known thrombocytopenia, based on platelet count < 50 x 10^9/L in the previous 3 months
  - g. Known hepatic disease, based on a medical history of elevated liver enzymes (3x ULN) and/or bilirubin (2xULN) documented within the last 3 months
  - h. Known renal failure, based on Creatinine Clearance < 30 mL/min (Cockcroft Gault) in the previous 3 months
  - i. Known severe hypertension, based on SBP > 200 mmHg and/or DBP > 120 mmHg in the previous 3 months
4. Received 7 or more doses of LMWH
5. Previous participation in the trial

6. Geographic inaccessibility\*\*
7. Refused consent

\*All other active or recent bleeding is at the discretion of the treating physician.

\*\*At the discretion of the patient or the treating physician

Note: Subjects currently receiving aspirin are eligible for the study.

Please note: Investigators should use caution when prescribing LMWH to patients with a history of gastric ulceration or whom weight >120kg or <45kg.

#### **4.3 Withdrawal of Subjects**

A subject has completed the study once all follow-up procedures have been completed.

Study drug is discontinued and appropriate clinical management is initiated in the case of the following outcome events (as defined in section 2.6). For the subjects who reach a study endpoint, LMWH and aspirin prophylaxis will be left up to the discretion of the treating physician, and documented.

1. Pregnancy loss
2. Pre-eclampsia
3. Placental abruption
4. Preterm delivery (<37 weeks)
5. VTE (objectively documented DVT, PE or sudden death)
6. Major bleeding
7. Thrombocytopenia (Platelet count <50 x 10^9/L)
8. Symptomatic fracture

In the event that the outcome does not result in infant delivery (ie. diagnosis of a VTE, fracture, thrombocytopenia, major bleed), antenatal follow-up will continue as scheduled in the protocol and data will be collected until 6 weeks post-partum or pregnancy related outcome.

A subject can be withdrawn from the trial treatment if, in the opinion of the investigator, it is medically necessary. This does not always correspond to study withdrawal – in which case antenatal follow-up will continue as scheduled in the protocol and data will be collected until the 6-12 weeks post-partum clinic visit, up until 6 weeks postpartum.

If the subject is prematurely discontinued from participation in the study, the study personnel will make every effort to obtain, and record, information about the reasons for discontinuation and any adverse events and if possible perform all safety assessments.

A subject may voluntarily withdraw participation in this study at any time, including for future data collection. If the subject does not return for a scheduled visit, every effort will be made to contact the subject. In any circumstance, every effort will be made to document the reason for withdrawal and when possible all safety assessments will be done.

[figure not shown]
All data will be reported for any subject randomized and not completing the study. Subjects withdrawn as a result of an adverse event thought to be related to the study drug will not be replaced. All safety data collected from all subjects during the study will be analyzed.

## **5. RECRUITMENT**

### **5.1 Treatment Schedule**

Upon enrolment into the study, subjects will be randomized to receive low dose aspirin alone until delivery, or low-dose ASA (until delivery) and prophylactic-dose LMWH until 37 weeks gestation or the onset of labour. The LMWH regime will be at the discretion of the treating physician, with a suggested regime as follows: tinzaparin 4,500 IU sc daily until 20 weeks gestation, and then 4,500 IU sc twice daily until 37 weeks gestation. Treating physicians will have access to other LMWHs as alternative 'standard of care' options, however, one regime is recommended for consistency (Figure 1). Dosing frequency after 20 weeks gestation is at the discretion of the treating physician based on practice-pattern differences, however, a twice daily dosing is recommended. The use of daily tinzaparin in the 6 week postpartum period is left to the discretion of the treating physician. Concomitant NSAID use is not recommended.

**Figure 1.** Recommended LMWH protocol

\*Alternatives include dalteparin 5,000 IU or enoxaparin 40 mg, however, tinzaparin 4,500 IU is preferred when possible.

Each subject will receive education regarding LMWH administration, potential adverse effects and symptoms of VTE by clinic personnel (not research personnel), based on standard of care.

### **5.2 Randomization**

Consenting subjects will be randomized up to 7 days after baseline visit. Treatment allocation is determined by central web-randomization. A randomization list has been generated by the trial statistician prior to embarking on the trial. Randomization is in permuted blocks of 10, prepared using random number tables, and is stratified according to laboratory criteria ('High-risk' versus 'Non-high risk' laboratory groups, defined below) and the timing of pregnancy loss (late loss versus no late loss) Any past history of loss  $\geq$  10 weeks gestation will be included in the late loss group.

**Definitions of groups:**

**No Late Loss:** Defined as only unexplained pregnancy loss(es) less than 10 weeks gestation

**Late loss:** Defined as one or more unexplained pregnancy loss(es) at or beyond the 10th week of gestation

**'Non-high risk' laboratory results are defined by both of:**

- 1) aCL of IgG and/or IgM positivity (>99th percentile)  $\leq$  40 GPL or MPL
- 2) No 'High risk' laboratory results present

**'High risk' laboratory results are defined by the presence of at least ONE of:**

- 1) Lupus anticoagulant present
- 2) aCL of IgG and/or IgM with a titre > 40 GPL or MPL
- 3) Anti-β2 glycoprotein antibody of IgG and/or IgM with a titre > 99th percentile

**Randomization groups:**

Non-high risk and no late loss: Group A

Non-high risk and late loss: Group B

High risk and no late loss: Group C

High risk and late loss: Group D

**5.3 Web Base Randomization**

The randomization process is started by the local study personnel (investigator or study coordinator) who initiates a randomization request by accessing the APPLE webpage and randomization request form. This portion of the webpage requires authorised users to enter a username and password. To randomize a subject the following information is required: category of 'high' versus 'non-high' risk laboratory criteria, and category of early versus late pregnancy loss. The program will request that the information entered be verified for accuracy and will prompt any errors or missing fields to be completed. When the information is accepted, the program will provide the delegated study coordinators, Qualified Investigator, and pharmacy team the treatment allocation by using the next allocation from that block.

**5.4 Study drug management**

The study drug (ASA and LMWH) will be dispensed by the local site hospital Pharmacy Department for all participants in both treatment arms. The local site hospital Pharmacy Department will be responsible for labeling, handling, and dispensing of the study drug.

**6. MEASUREMENTS AND EVALUATIONS**

**6.1 Demographic and Baseline Characteristics (Baseline Period)**

Subjects will be required to sign a consent form prior to any study procedures being undertaken. During the baseline period, before randomization (up to 11 weeks + 6 days gestation), the following information will be measured and/or recorded:

- Demographic data:
  - Age and birth month
  - Race/Ethnicity

- Height and weight prior to pregnancy
- Current pregnancy data:
  - Gestational age/estimated date of delivery
  - Type of test used to confirm pregnancy and date performed
  - Method of conception
  - Number of fetuses
- Medical history:
  - Presence of SLE diagnosed by rheumatologist or internist
  - Presence of livedo reticularis
  - Presence of hypertension
  - Presence of type 1 diabetes
  - Presence of type 2 diabetes
  - Smoking status
  - Known inherited thrombophilia present and details
- Obstetrical History:
  - Age at start of each pregnancy
  - Gravida, term deliveries, premature deliveries, spontaneous abortions, therapeutic abortions, living children and multiple pregnancies
  - Number, timing and reason of past pregnancy losses
    - According to < 10 weeks, ≥ 10 weeks
  - Past pregnancy complications
    - Pre-eclampsia, SGA, placental abruption, pre-term delivery
  - Treatment of past pregnancies (use of LMWH and/or ASA)

## **6.2 Laboratory and Imaging Assessments**

A baseline BHCG will be drawn at the screening period, if not already available for the current pregnancy. A CBC and creatinine will be drawn at baseline, if not previously available within the past 3 months. A second set of antiphospholipid labs can be drawn if required to meet the eligibility laboratory criteria, 12 weeks apart from the first set. The subject can be enrolled and randomized to a treatment arm prior to receiving the second set of lab results. According to the diagnostic criteria of APS, diagnosis should be avoided if more than 5 years is separated between positive antibody testing and a clinical manifestation, such as pregnancy loss.

Within 7 days of enrollment, a baseline obstetrical ultrasound is recommended. If the subject is enrolled in early first trimester (<6 weeks gestation) then the ultrasound will be completed at 6-7 weeks gestation. Blood work will also be drawn on enrollment and stored and tested in a central laboratory (lupus anticoagulant, anticardiolipin IgG and IgM antibodies, beta-2 glycoprotein IgG and IgM antibodies).

Additional blood work or imaging assessments will be ordered if an outcome is clinically suspected, and will be left up to the discretion of the treating physician.

## **6.3 Prior and Concomitant Therapy**

Concomitant therapy will be at the discretion of the primary physician. Selected concomitant medications will be documented on the case report forms. Investigators who decide to discontinue antenatal LMWH at 37 weeks gestation and initiate the use of unfractionated heparin will be required to document this on the concomitant medication record in the case report form. NSAID use is not recommended.

#### **6.4 Antenatal Follow-up**

Antenatal follow-up will occur at 20 ( $\pm 4$ ) weeks gestation and the following information will be recorded:

- Gestational age
- Medication regime plan
- Medication compliance
- Possible adverse events and outcomes

#### **6.5 Postpartum Follow-up**

Postpartum follow-up will occur at 6-12 weeks postpartum and the following information will be recorded:

- Number of weeks postpartum at time of visit
- Postpartum medication regime plan (if applicable)
- Epidural use during labour
- Medication compliance
- Possible adverse events and outcomes

#### **6.6 Labour and Delivery Record**

Available labor and delivery information will be recorded:

- Date of delivery
- Gestational age at delivery
- Mode of delivery
  - Vaginal delivery versus caesarian section, including reason for C-section (scheduled versus unscheduled/emergency)
- Estimated blood loss in mL, if available
- Spontaneous versus induction of labor, and reason for induction if available
- Live birth
- Infant data
  - Sex, weight and percentile
  - NICU admission
  - Infant survival (record cause if known)

#### **6.7 Adjudication**

A blinded adjudication committee will be assembled to review the following suspected outcomes: pre-eclampsia, placental abruption, symptomatic VTE, symptomatic ATE, suspected bleeding, suspected HIT and/or death.

Each suspected event will be reviewed by two committee members to determine if it meets the criteria for the full trial outcomes as outlined in the protocol. If the two reviewers disagree, a third member will review to act as a tie-breaker.

All relevant medical records, imaging results, etc. will be collected to prepare an adjudication report.

#### **6.8 Adverse Events**

AEs will be elicited, monitored and recorded throughout the study. For each subject, AEs will be submitted to the trial office following visits at gestational week 20  $\pm$  4 weeks, labour and delivery, and 6-12 weeks postpartum.

### Pre-existing Conditions

In this trial, a pre-existing condition (i.e., a disorder present before the AE reporting period started and noted on the pre-treatment medical history/physical examination form, this will include pregnancy) is not to be reported as an AE unless the condition worsens or episodes increase in frequency during the AE-reporting period.

### Procedures

Diagnostic and therapeutic non-invasive and invasive procedures, such as surgery, are not to be reported as AEs. However, the medical condition for which the procedure is performed is to be reported if it meets the definition of an AE. For example, an acute appendicitis that begins during the AE reporting period is to be reported as the AE and the resulting appendectomy noted under Comments.

### **7.2 Eliciting Adverse Event Information**

The investigator is to report all directly observed AEs and all AEs spontaneously reported by the trial subject. In addition, each trial subject will be questioned about AEs at each clinic visit following initiation of treatment

### **7.3 Adverse Event Reporting Period**

The AE reporting period for this trial begins upon randomization, and ends 30 days after receiving the last dose of trial medication. The AE reporting period for neonates begins upon randomization and ends 30 days after the subject has received the last dose of trial medication.

**All AEs that occur in trial subjects during the AE reporting period specified in the protocol must be recorded in the CRF, WHETHER OR NOT THE EVENT IS CONSIDERED MEDICATION/PRODUCT RELATED.**

IN ADDITION, any known untoward event that occurs subsequent to the AE reporting period that the investigator assesses as possibly related to the investigational medication/product is also to be reported as an AE.

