#### Experimental arm

Open-label low-dose aspirin daily from randomization until delivery

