#### Standard of care arm

Open-label LMWH prophylaxis until 37 weeks gestation **AND** low-dose aspirin daily until delivery.

The recommended "standard of care" arm is tinzaparin 4,500 IU sc daily until 20 weeks gestation, then tinzaparin 4,500 IU sc twice daily until 37 weeks gestation and aspirin 81 mg po daily until delivery. Treating physicians do have access to other LMWH (dalteparin, enoxaparin) as standard of care, but the suggested regime with tinzaparin is recommended. The use of LMWH prophylaxis beyond 37 weeks gestation and in the 6 week postpartum period will be left up to the discretion of the treating physician.

Each subject will receive education regarding LMWH administration, potential adverse effects and symptoms of VTE by clinic personnel (not research personnel), based on standard of care.

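### Adverse-event reporting, including for neonates, is timed from the mother's last dose instead of from birth, so for a woman who stops all trial medication early it can close before the baby is born

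*Combined protocol and SAP*

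**What the plan says.** Section 7.3 sets the maternal adverse-event (AE) period as one that "begins upon randomization, and ends 30 days after receiving the last dose of trial medication". For the infant it says: "The AE reporting period for neonates begins upon randomization and ends 30 days after the subject has received the last dose of trial medication". Both windows therefore run between two maternal dates, randomization and last dose. Birth is not used. After the window closes, 7.3 still requires reporting of "any known untoward event that occurs subsequent to the AE reporting period that the investigator assesses as possibly related" to the investigational product.

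The planned treatment runs to delivery in both arms. The synopsis gives the experimental arm as "Open-label low-dose aspirin daily from randomization until delivery", and the standard of care arm as LMWH to 37 weeks plus "low-dose aspirin daily until delivery". Section 5.4 treats both ASA and LMWH as study drug.

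Section 4.3 provides for earlier stopping: "Study drug is discontinued and appropriate clinical management is initiated in the case of the following outcome events". It lists eight such events and also lets the investigator withdraw a woman from treatment without withdrawing her from the study. Where the event does not lead to delivery, follow-up and data collection go on to 6 weeks postpartum.

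Other sections describe AE collection differently. Section 6.8 says "AEs will be elicited, monitored and recorded throughout the study", with submission after the week 20, delivery and 6-12 week postpartum visits. The schedule of mandatory events and Table 1 in section 7.6 name the same three time points. For outcome events there is a fixed end: under section 3.5, "outcome events will be recorded up until 6 weeks postpartum".

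**The concern.** A neonatal safety window ought to contain the neonatal period. Under 7.3 it does so only if the mother's last dose is close enough to delivery. Several of the section 4.3 stopping events (VTE, major bleeding, thrombocytopenia, fracture) need not end the pregnancy. For these women the plan continues follow-up to 6 weeks postpartum, yet its AE rule can close the recording period while they are still pregnant.

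There is also an operational problem. A site applying 7.3 would leave an unrelated event at 4 weeks postpartum in an early stopper off the AE form, while a site applying 6.8 and the visit schedule would record it. Each could claim to be following the protocol. Pilot data may be carried into the full trial (sections 2.1 and 8.1.4), for which section 2.4 promises a report of bleeding and other adverse events. An inconsistent collection rule would be carried forward with them.

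**Working it through.** The plan states no figure to reproduce; the check is calendar arithmetic.

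**Inputs from the protocol.** Window end = last dose + 30 days (7.3). Planned last dose = aspirin to delivery in both arms (synopsis, 5.1). Outcome events end at 6 weeks = 42 days postpartum (3.5).

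**Assumptions not in the protocol.** Birth at 40 weeks (280 days), with 37 weeks (259 days) as the lower case; illustrative stopping times between 12 and 34 weeks. The last dose here means the last dose of any trial medication.

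**Formula.** Closing day (gestational) = 7 × week of last dose + 30. Distance from birth = closing day − 7 × week of birth.

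For a last dose at 20 weeks: 7 × 20 + 30 = 170 days = 24 weeks + 2 days, and 170 − 280 = −110 days.

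| Last dose | Window closes | Birth at 40 weeks | Birth at 37 weeks |
|---|---|---|---|
| 12 weeks | 16w2d | 166 days before | 145 days before |
| 20 weeks | 24w2d | 110 days before | 89 days before |
| 28 weeks | 32w2d | 54 days before | 33 days before |
| 34 weeks | 38w2d | 12 days before | 9 days after |
| At delivery (as planned) | – | 30 days after | 30 days after |

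**Latest harmless stopping time.** The window reaches birth only if the last dose is at or after 280 − 30 = 250 days = 35w5d (birth at 40 weeks), or 259 − 30 = 229 days = 32w5d (birth at 37 weeks).

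**Planned course.** The window closes 30 days after delivery in both arms, 42 − 30 = 12 days before outcome recording ends.

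**Which drug sets the last dose.** Section 7.3 does not say. Section 5.4 counts both drugs, which makes aspirin the last one on the planned course. But section 3.3 describes use of trial medication beyond 37 weeks as discretionary, which fits LMWH and not aspirin. If a site took the last LMWH dose at 37 weeks, the window would close at 259 + 30 = 289 days = 41w2d, 9 days after a 40-week birth. If 6 weeks of discretionary postpartum LMWH counted as trial medication, it would close 42 + 30 = 72 days after birth.

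**What other rules still capture after the window closes.**
- Neonatal deaths in the first month of life, whatever the cause, and congenital anomalies (7.5).
- The named full-trial outcomes to 6 weeks postpartum (3.5, schedule of events).
- NICU admission and infant survival on the delivery record (6.6).
- Later events that become known and are judged possibly related (7.3).

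What remains is other maternal and neonatal AEs judged unrelated. Because section 7.5 defines a serious event as a subset of AEs, an unrelated hospitalization after the window may also fall outside 24-hour reporting and DSMB review under 7.6.

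**The case against.** The strongest reply is that the planned course has no gap before birth. Both arms take aspirin to delivery, so the window extends about 30 days beyond it. That stands, and it confines the problem to women who stop all trial medication early and remain pregnant.

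That group may be small. Of the eight stopping events, pregnancy loss and preterm delivery end the pregnancy (multiple pregnancies aside), and section 2.6 defines abruption as leading to delivery. After an endpoint, section 4.3 leaves LMWH and aspirin to the treating physician, so some women may continue. The pilot has only 24 participants, and the documents give no stopping rate. All of this stands, but it limits how often the rule fails; it does not make the rule right.

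The capture rules listed above, and AE questioning at each clinic visit (7.2), are also real protection. A reader might infer that serious neonatal harm would go unrecorded; the documents do not support that. The residual gap depends on a relatedness judgement made by an investigator who knows the allocation.

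A reader might further infer that the planned comparison of AEs between arms is biased, since observation time follows drug exposure. The documents do not support that either. The planned last drug is the same in both arms, nothing shows unequal stopping, and section 8.1.4 tests only named outcomes, which are recorded to 6 weeks postpartum whatever the exposure. An arm difference would arise only if sites read the last dose as the last LMWH dose, or if stopping proved unequal.

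**Conclusion.** The concern holds for early stoppers. Followed literally, 7.3 can end neonatal AE reporting before there is a neonate: 110 days before birth for a last dose at 20 weeks and birth at 40 weeks, or 89 days before for birth at 37 weeks. It also disagrees with section 6.8, the schedule of events and Table 1, which collect AEs at delivery and at 6-12 weeks postpartum. On the planned course the consequence is only a window 12 days shorter than outcome recording, equal in both arms.

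The loss is mainly of other maternal and neonatal AEs, including serious ones, that are judged unrelated. The primary feasibility endpoint and the tests in 8.1.4 are unaffected. The figures rest on the assumed birth and stopping times and on counting both drugs as trial medication; how many women would be affected cannot be estimated from the documents. It is worth correcting because the stated rule gives the wrong result in a situation the protocol itself foresees, and the correction is cheap.

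**What to change.** Amend section 7.3 as follows; this changes data collection only, not treatment.

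- **Maternal AEs:** from randomization to the later of (a) 6 weeks postpartum, or 6 weeks after a pregnancy loss, and (b) 30 days after the last dose of trial medication.
- **Fetal and neonatal AEs:** keep the start at randomization and end no earlier than 6 weeks after birth.
- **Late events:** keep the existing clause on possibly related events.
- **Definition:** state which drug sets the last dose (ASA, LMWH or either) and whether discretionary postpartum use counts.
- **Consistency:** reconcile 7.3 with 6.8, the schedule of mandatory events and Table 1.

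The later-of-two-dates form matters. A flat 6-week cut-off would reduce coverage from 72 to 42 days after birth if 6 weeks of postpartum drug counts as trial medication. For the woman who stops at 20 weeks and delivers at 40, the new rule extends the maternal window from day 170 to day 280 + 42 = 322, a gain of 152 days.

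The cost is a wording amendment and slightly more AE recording at the existing 6-12 week postpartum visit. After a pregnancy loss one additional contact may be needed, because the only late visit is defined as postpartum.
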